9.1 STATISTICAL HYPOTHESES

- Primary Feasibility, Acceptability, Fidelity Endpoint(s): RE-PACT's primary outcomes will be analyzed descriptively, and evaluate feasibility, acceptability, fidelity using multiple approaches. Each outcome will be

assessed against our pre-specified measures of success, e.g., achieving at least 80% enrollment. By conducting iterative refinements over three waves of implementation, we expect to achieve success in all measures. We will assess all participant feedback using both quantitative and qualitative data to determine what study design changes would enhance a large-scale RCT. We will use inductive content analysis of qualitative data.

- Secondary Efficacy Endpoint(s): **To inform a future large multisite RCT, we will test** differences between treatment (I or AC) groups in the primary and secondary respiratory illness outcomes. Our goal with these analyses is to estimate effect sizes for the differences between groups. The primary clinical outcome is severe respiratory illness rate, defined as the total number of severe respiratory illnesses divided by the person-months over the 6 months period. The severe respiratory illness rate will be analyzed with negative binomial (NB) regression models to account for overdispersion in the count data. In the primary analysis, univariate NB regression analysis will be conducted with study arm as a predictor variable. Study site will be a stratification factor to account for stratified randomization. The observed effect size of the analysis will be quantified in terms of relative risk (RR) and reported along with the corresponding 95% confidence interval. A generalized linear mixed effects model with a logit link function and subject specific random effects will evaluate **longitudinal changes** in the severe respiratory illnesses within and between study arms. An autoregressive (AR) correlation structure will account for within subject correlations. In this analysis, presence/absence of severe respiratory illness at the monthly assessments will be the dependent variable; study arm will be included as a predictor variable, and study site as a stratification variable to account for the stratified randomization. **To investigate theoretical mechanisms**, we will test the mediating effect of caregiver capability, opportunity, and motivation (COM-B)¹¹³ measures on the relationship between intervention and respiratory exacerbations.

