9.4 STATISTICAL ANALYSES

9.4.1 GENERAL APPROACH

This section outlines the statistical analysis strategy and procedures for the study. We plan to use the primary outcome data to assess the RE-PACT intervention's feasibility, acceptability, and fidelity. We anticipate being underpowered to assess efficacy using the clinical endpoints of the intervention in this pilot study. The clinical outcome endpoints will be used to develop an estimate of effect size. Categorical variables will be displayed as percentages, and continuous variables as means with standard deviations (if normally distributed) or medians with IQR (if skewed). For inferential statistics, two-sided p-values <0.05 will be considered statistically significant. A detailed Statistical Analysis Plan (SAP) describing all details of the analyses has been developed and will be finalized prior to the database lock and the analysis of the final study data.

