9.4.3 ANALYSIS OF THE SECONDARY ENDPOINT(S)

Clinical Outcomes. We will test differences between treatment (intervention or control) groups in the primary and secondary respiratory illness outcomes. Our goal with these analyses is to estimate effect sizes for the differences between groups which will allow precise sample size calculations for a future large-scale trial.

Primary clinical outcome is the severe respiratory illness rate, defined as the total number of severe respiratory illnesses divided by the person-months over the 6-month follow-up period. The severe respiratory illness rate will be analyzed using a negative binomial (NB) regression model to account for overdispersion in the count data. For the primary analysis, univariate NB regression analysis will be conducted with study arm as a predictor variable. Study site will be included as a stratification factor in the primary analysis to account for stratified randomization. The observed effect size of the analysis will be quantified in terms of relative risk (RR) and reported along with the corresponding 95% confidence interval.

As a secondary analysis, multivariate NB regression analysis will be performed to compare the severe respiratory illness rates between study arms. In this analysis, clinical and demographic characteristics will be included as covariates in an initial non-parsimonious model. The least absolute shrinkage and selection operator (lasso) and elastic net penalty methods for negative binomial regression models will be utilized to identify a parsimonious model with independent covariates. These methods are considered state-of-the art techniques for variable selection (Wang Z., et al. Stat Methods Med Res. 2016).

Longitudinal changes in the severe respiratory illnesses within and between study arms, will be evaluated with generalized linear mixed effects model with a logit link function and subject specific random effects. An autoregressive (AR) correlation structure will be utilized to account for within subject correlations. In this analysis, the presence/absence of severe respiratory illness at the monthly assessments will be the dependent variable, study arm will be included as a predictor variable and study site as a stratification variable to account for the stratified randomization.

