Secondary clinical outcomes include total hospital days during severe respiratory illness, numbers of systemic steroid courses, systemic antibiotic courses, respiratory ED visits and death. The numbers of systemic steroid courses, systemic antibiotic courses, and respiratory ED visits over the 6 months follow-up period will be analyzed using NB regression analyses in a similar fashion as described above for the primary outcome. Observed effect sizes will be reported along with the corresponding 95% confidence intervals. The presence/absence of systemic steroid courses, systemic antibiotic courses, and respiratory ED visits will be documented at the monthly assessments and longitudinal changes within and between study arms will be analyzed using generalized linear mixed effects modeling with a logit link function and patient specific random effects. The total number of hospital days over the 6 months follow-up period will be analyzed using analysis of variance (ANOVA) with study site as stratification factor. In a secondary analysis, analysis of covariance (ANCOVA) will be performed where clinical and demographic baseline characteristic will be included as covariates and the lasso method will be used to identify a parsimonious

model. Longitudinal changes in the number of hospital days per hospitalization will be analyzed using a normal mixture linear mixed effects model with patient specific random effects. The normal mixture component will be included in the model to capture the probabilities of a hospitalization at the monthly follow-up. Parameter estimation will be performed using the Expectation-Maximization algorithm which is the standard method for parameter estimation of mixture models.

Missing values, e.g., due to loss of follow-up, missing monthly visits, will be evaluated by conducting a sensitivity analysis comparing the results obtained from the complete case analysis to the results obtained by imputation-based analyses. Specifically, multiple imputation (MI) will be used to impute missing values of primary and secondary clinical outcomes. For monotonic missing values data structures, we will use regression-based MI techniques. For non-monotonic missing value data structure, on the other hand, we will use Markov Chain Monte Carlo based imputation techniques.

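### The logistic mixed model meant to show change over time in severe respiratory illness lists arm and site but no month or arm-by-month term, so as written it yields only a month-averaged odds ratio

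*Combined protocol and SAP*

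**What the plan says.** Section 9.4.3 gives the aim: "Longitudinal changes in the severe respiratory illnesses within and between study arms, will be evaluated with generalized linear mixed effects model". It has a logit link and subject-specific random effects. The outcome is binary and repeated: "the presence/absence of severe respiratory illness at the monthly assessments will be the dependent variable". The predictors are then named: "study arm will be included as a predictor variable and study site as a stratification variable to account for the stratified randomization". On correlation it says: "An autoregressive (AR) correlation structure will be utilized to account for within subject correlations". Section 9.1 describes the same model with the same predictors: "study arm will be included as a predictor variable, and study site as a stratification variable to account for the stratified randomization". Neither section mentions month, time or an arm-by-time interaction.

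For steroid courses, antibiotic courses and respiratory ED visits, 9.4.3 states: "longitudinal changes within and between study arms will be analyzed using generalized linear mixed effects modeling with a logit link function". It adds patient-specific random effects. It names no fixed effects for these three outcomes and no autoregressive structure.

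Section 9.4.1 refers to a fuller document: "A detailed Statistical Analysis Plan (SAP) describing all details of the analyses has been developed and will be finalized prior to the database lock". The supplied text contains no time term for any of these models.

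**The concern.** The aim and the listed model do not match. To show change within an arm, the mean model needs a term that varies with month. To show that change differs between arms, it needs an arm-by-month term. The specification gives the outcome, link, random effects, correlation structure, predictor and stratifier, in two places, but not the terms that define its purpose.

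An analyst who follows the text would report a month-averaged odds ratio as if it described change over time. An analyst who adds month must choose its form later (linear, categorical, with or without interaction), and 9.4.1 sets a 0.05 significance threshold for inferential results. Either way, the written plan does not determine the answer to its own question.

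**Working it through.** The plan states no figure for the longitudinal models, so there is none to reproduce. The check has three parts.

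**1. What the listed model can represent.**

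As written: logit(p) = b0 + b1·arm + b2·site + subject effect.

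- Nothing on the right changes with month. Over arm × site × six months the fixed-effect design has rank 3.
- The autoregressive structure describes how a child's months correlate, and the random effect has mean zero. Neither adds a trend to the mean.
- Adding month and arm × month raises the rank to 5.

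**2. Illustration with assumed trajectories.**

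Control risk is flat at 1/12 = 0.083 per month, from the one illness per child-year in 9.2. Intervention risk follows three invented paths, scaled to the same six-month mean of 0.083. The fits are fixed-effect logistic, without random effect or autoregression.

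| Intervention risk, month 1 to 6 | As written: fitted monthly risk | As written: arm OR | With the two terms: arm-by-month OR per month |
|---|---|---|---|
| Flat | 0.0833 in all months | 1.00 | 1.00 |
| Falling, about 0.14 to 0.03 | 0.0833 in all months | 1.00 | 0.74 |
| Rising, about 0.03 to 0.14 | 0.0833 in all months | 1.00 | 1.35 |

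The listed model returns the same answer for three opposite histories. The extended model separates them.

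**3. How precise the corrected trend would be.**

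Inputs:
- 45 per arm with 10% missing (9.2): 45 × 0.9 = 40.5.
- One illness per year (9.2): six-month mean 0.5.
- Overdispersion 1.0 (9.2).
- Assumption: an intervention mean of 0.3, borrowing the 40% lower hospitalization rate reported for the earlier PACT trial in 2.2.

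Monthly prevalence under a gamma-Poisson model is 1 − 1/(1 + mean/6):
- Control: 1 − 1/1.0833 = 0.077.
- Intervention: 1 − 1/1.05 = 0.048.

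Months 1 to 6 have a sum of squared deviations of 17.5. Ignoring within-child correlation:

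- SE of the slope difference = √[1/(40.5 × 0.077 × 0.923 × 17.5) + 1/(40.5 × 0.048 × 0.952 × 17.5)] = √(0.0199 + 0.0309) = 0.225 per month.
- Over five months: 5 × 0.225 = 1.13.
- 95% interval factor: exp(1.96 × 1.13) ≈ 9.1 either way.

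That is one scenario. Simulation with 40 per arm, using the empirical spread of the fitted slope difference, gives a wide range:

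| Six-month means, control / intervention | Month 1 to 6 factor |
|---|---|
| 1.0 / 0.6 | about 5 |
| 0.5 / 0.5 | about 8.5 |
| 0.5 / 0.3 | about 12 |
| 0.5 / 0.167 (rate ratio 3, the smallest in the 9.2 table) | about 31 |

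The first row is included because 9.2 also expects half of participants to have at least one respiratory illness. With overdispersion 1.0, a mean of 0.5 gives 1 − 1/1.5 = 33%, while a mean of 1.0 gives 1 − 1/2 = 50%. Section 9.2 does not say whether that half refers to severe illness.

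**Information on within-child correlation.** In the same simulation 9.8% of children at mean 0.5 and 4.6% at mean 0.3 have illness in two or more months. That is 40.5 × 0.098 + 40.5 × 0.046 ≈ 4.0 + 1.9, about 6 children, or 81 × 0.098 ≈ 8 if both arms are at 0.5.

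**The case against.** The strongest reply is that this is shorthand. Neither section calls its predictor list complete, the stated aim and monthly outcome suggest that month was intended, and 9.4.1 points to a detailed SAP that may supply it. Part of this stands. A reader might infer that the plan excludes time; the documents say no such thing. The supportable statement is that the time terms are not stated and that the model, fitted as written, has no trend parameter.

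Four other stronger readings also fail:

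- **That all four logistic models contain only arm and site.** This is true of severe respiratory illness. For the other three outcomes no fixed effects are listed, so the gap there is a missing specification.
- **That a random effect and an autoregressive structure cannot be separated in these data.** The two imply different correlation patterns (constant and decaying across lags), and no model with both was fitted here. With about 6 to 8 children having repeat-event months, separation would be fragile. That supports a fallback rule, not a ban, and applies only to the severe respiratory illness model, the only logistic model with an autoregressive term.
- **That the interval factor is about 9 on the plan's own figures.** It depends on an assumed intervention rate, and no rates are given for steroid courses, antibiotic courses or ED visits.
- **That the efficacy result is compromised.** The clinical effect size comes from the negative binomial rate model, the primary endpoints are descriptive, and the plan says that it expects to be underpowered.

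A fair further objection is that adding terms may not be enough. The schedule in 1.3 lists monthly study assessments under the intervention arm only, and 5.5 describes monthly contact for intervention subjects, with control subjects contacted at baseline and six months. The synopsis speaks of clinical outcomes at monthly intervals without limiting this to one arm. This stands, and the fix must address it.

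**Conclusion.** The point holds for the model as written. In 9.1 and 9.4.3 the listed predictors for monthly severe respiratory illness cannot answer the stated question about change over time; they give one odds ratio averaged over months. For the three other monthly outcomes the aim is stated without any fixed effects. Nothing in the supplied text fills the gap, and the detailed SAP is described as not yet final.

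The structural conclusion needs no assumption about rates. The precision figure does: a factor of roughly 5 to 30 either way rests on a gamma-Poisson model with overdispersion 1.0, about 40 children per arm, and six-month means of 0.5 to 1.0 in control and 0.167 to 0.6 in intervention. Across that range the corrected trend is suited to description, not testing.

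Priority is moderate. The average between-arm contrast survives, and the main clinical analysis and primary endpoints do not depend on this model.

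**What to change.** In 9.1, 9.4.3 and the SAP, before it is finalized:

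1. Specify arm + month + arm × month + site for each monthly logistic model (severe respiratory illness, steroid courses, antibiotic courses, respiratory ED visits). State the form of month in advance. At the prevalences above, 40.5 × 0.077 ≈ 3 control and 40.5 × 0.048 ≈ 2 intervention children would be affected in a given month, which favours a linear term over six categories.
2. Report arm-specific trends and the interaction with 95% intervals as descriptive results.
3. State that month-level outcomes in both arms come from the same source, such as dated chart review; 4.1 already has all participants authorize access to the child's record. Reconcile this with 1.3 and 5.5.
4. For severe respiratory illness only, pre-state a fallback to a single correlation device if the model with random effect and autoregression does not converge. If the fallback is GEE, note that its odds ratio is population-averaged, not subject-specific, and that unweighted GEE needs stronger missing-data assumptions.

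Alternatively, drop the claim about change over time and describe the result as an average between-arm contrast.

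The model terms cost only wording. Item 3 may cost more if dated control-arm chart review is not already planned. The other cost is that the reported trend intervals will be very wide.

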9.2 SAMPLE SIZE DETERMINATION

We will enroll a total of 90 participants. Wave 1 will contain 10 participants (5 UW, 5 UCLA); Wave 2 will contain 20 participants (10 UW, 10 UCLA); Wave 3 will contain 60 participants (30 UW, 30 UCLA). Based on this team's preliminary work, eligible children average one severe respiratory illness per year and we estimate 50% of participants will experience at least one respiratory illness during the period of enrollment. We expect to be able to maintain contact and collect data from ≥90% of the participants at the final follow-up, evenly divided between intervention and control groups. We assume this sample will not be powered to establish the efficacy of the intervention; however, it will provide a sufficient sample to determine feasibility and estimate effect sizes which will be used for power calculations in the future large RCT. The following table shows the attainable power levels for detecting various differences in severe respiratory illness rates (primary clinical outcome) between study arms at the two-sided 0.05 significance level, based on a NB regression model with an overdispersion parameter of $\phi=1.0$.

Attainable power levels for detecting differences in severe respiratory illness rates between arms at the two-sided 0.05 significance level based on a NB regression model, assuming a sample size of 45 subjects per arm with a missing value rate of 10% or less.

Relative Risk (RR)	Number of severe respiratory illnesses in intervention arm over 6-month Follow-up period				
	5	10	15	20	25

(Control vs. Intervention) ($\lambda=0.02$)*	($\lambda=0.40$)*	($\lambda=0.06$)*	($\lambda=0.08$)*	($\lambda=0.10$)*
3.0	19%	29%	38%	45%
4.0	31%	41%	59%	68%
5.0	42%	62%	74%	83%

*Severe respiratory illness rate per patient-month

Hence, large effect sizes with RRs ranging between 3.0-5.0 for comparing the severe respiratory illness rates between study arms will be detected with 19-88% power at the two-sided 0.05 significance level.

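### The longitudinal model for hospital days puts a normal mixture on months without an admission, which are exact zeros or undefined; a two-part model should replace it

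*Combined protocol and SAP*

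**What the plan says.** The relevant text is in Section 9.4.3, under the secondary clinical outcomes. "Longitudinal changes in the number of hospital days per hospitalization will be analyzed using a normal mixture linear mixed effects model". The model also includes a random effect for each child. On the mixture: "The normal mixture component will be included in the model to capture the probabilities of a hospitalization at the monthly follow-up". On fitting: "Parameter estimation will be performed using the Expectation-Maximization algorithm which is the standard method for parameter estimation of mixture models".

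The text does not say:
- whether the no-hospitalization component is a normal or a point mass at zero;
- whether the components have separate or common variances;
- what value a month without an admission takes.

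The same section separately plans an ANOVA of total hospital days over six months, with site as stratification factor, and a logistic mixed model for monthly presence or absence of severe respiratory illness.

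Section 9.2 gives two event figures. The first is a rate: "eligible children average one severe respiratory illness per year". The second is a proportion: "we estimate 50% of participants will experience at least one respiratory illness during the period of enrollment". This second figure is not limited to severe illness. Section 9.4.1 says that a detailed SAP will be finalized before database lock.

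**The concern.** A latent mixture is useful when class membership is unknown. Here it is known: Section 8.1 defines the event by hospitalization and discharge diagnosis, so each month either contains an admission or does not.

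The two halves of the specification also conflict. If the mixture is to carry the monthly probability of hospitalization, months without an admission must be in the data. In those months days per hospitalization has no value, or is exactly zero if total days are used instead. A normal distribution is unsuitable for a block of identical zeros, and length of stay in the remaining months is positive and likely to be right-skewed.

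At stake is whether this analysis returns what it is meant to return. Section 9.4.3 says the clinical analyses supply effect sizes for sizing the next trial. As written, the answer depends on choices the plan does not make, such as the variance structure or a numerical floor.

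**Working it through.** The plan states no zero share and no result for this model, so there is no figure to reproduce.

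**Inputs.** From Section 9.2: 90 children, 45 per arm, up to 10% missing, overdispersion 1.0, and the two event figures above. Follow-up is 6 months, so 90 × 6 = 540 child-months. Assumed, because the documents give no distribution: lognormal stay, median 5 days, log-SD 0.8.

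**1. Share of child-months without an admission.**
- One per year is 1/12 = 0.083 per month. Poisson: exp(-0.083) = 92.0%. Negative binomial: 1/(1 + 0.083) = 92.3%. In 500 simulated trials the mean was 92.3% (95% range 89.4-94.6%).
- 50% with at least one illness in 6 months. Constant monthly risk: 0.5^(1/6) = 89.1%. Negative binomial: 1/(1 + μ) = 0.5 gives μ = 1 over 6 months, so 1/(1 + 1/6) = 85.7%.
- Extremes of the power table, arms pooled. Rates 0.02 and 0.06: (1/1.02 + 1/1.06)/2 = 96.2%. Rates 0.10 and 0.50: (1/1.10 + 1/1.50)/2 = 78.8%.

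**2. Separate variances.** For n₀ exact zeros and a component with weight π, mean 0 and SD s, the log-likelihood contains n₀[ln π − ln s − ½ ln(2π*)], where π* = 3.14159. The other component keeps the non-zero months finite, so the total goes to infinity as s goes to 0. Each tenfold cut in s should add n₀ × ln 10. The first simulated data set had 540 − 39 = 501 zeros, and 501 × 2.3026 = 1153.6.

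| SD of zero component | Log-likelihood |
|---|---|
| 1 | −675.6 |
| 0.1 | 435.1 |
| 0.01 | 1588.4 |
| 0.001 | 2741.9 |
| 0.000001 | 6202.7 |

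From 0.01 to 0.001 the gain is 1153.5, as predicted. Unconstrained EM became non-finite after 4-5 iterations in all three simulated data sets.

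**3. Random intercept.** It does not cure this. A child with six zeros contributes −7.1, 4.4, 15.9 and 27.4 at SD 1, 0.1, 0.01 and 0.001. Each step adds about 11.5 = 5 × 2.3026: the intercept absorbs one of the six zeros and the other five still diverge.

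**4. Common variance.** The likelihood is bounded and EM converges, but to the wrong split (EM fitted without random effects).

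| Data set | True monthly probability | Fitted | Factor too low | True mean days, admitted months | Fitted mean |
|---|---|---|---|---|---|
| 1 | 7.2% | 2.6% | 2.8 | 6.1 | 11.8 |
| 2 | 9.3% | 0.7% | 12.5 | 8.1 | 40.5 |
| 3 | 7.2% | 2.0% | 3.6 | 8.8 | 19.9 |

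Factors use unrounded shares. The second component holds only the longest stays; shorter ones are absorbed by the zero component. Six further simulated data sets gave a fitted probability of 1.5-4.3% against a true 5.2-7.9%.

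**5. Adding a floor.** With separate variances and an SD floor of 0.01, EM gives zero shares of 0.928, 0.907 and 0.928 and non-zero means of 6.10, 8.05 and 8.84. The two-part values are 0.928, 0.907, 0.928 and 6.10, 8.06, 8.85. A floor of 0.5 shifts the means to 6.60, 9.02 and 9.27.

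**6. Information on days.** At one event per year, 540 × 0.077 = 42 admission-months are expected. With 10% loss, and the 40% reduction seen in the earlier PACT trial (Section 2.2) assumed for the intervention arm, 243 × 0.0769 + 243 × 0.0476 = 30. The chance of two or more admissions in 6 months is [μ/(1 + μ)]². At μ = 0.5 it is 11.1%, or 9 of 81 children. At μ = 1 (the 50% figure) it is 25%, or about 20 of 81. Patient random effects for days would rest on those children.

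**The case against.** The strongest reply is that Section 9.4.3 is underspecified rather than wrong. It never says that the no-hospitalization part is a normal or that variances differ. A mixture meant to capture the probability of hospitalization could be read as zero versus non-zero, and the detailed SAP may say so. That stands in part: unboundedness needs separate variances. But the text names a normal mixture, and both normal readings fail, one by collapse and the other by misclassification. The point-mass reading is the two-part model proposed here.

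A second reply is that if days are undefined without an admission, no zeros enter and nothing collapses. True, but then every record has a hospitalization and the mixture cannot carry its probability.

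A reader might infer that no usable estimate can result, or that the answer would be arbitrary. The calculations do not support this. With a small SD floor the estimates match the two-part ones, and repeated runs from four starting points with floors from 0.0001 to 0.1 agreed within each data set. What diverges is the likelihood and one nuisance SD. The floor is, however, an unplanned step.

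A reader might also take a zero share above 90% as the plan's own figure. The documents state none, and it follows from only one of the two event figures. Stays crossing a month boundary would lower it further.

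Finally, a two-part model compares days only among admitted children, a subset formed after randomization. That stands, and the fix must say so.

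**Conclusion.** The concern holds in limited form. A normal mixture is the wrong model for an outcome that is undefined or exactly zero in roughly 86-92% of child-months under the two figures in Section 9.2. With separate variances, degeneracy follows from repeated exact zeros alone; it needs neither a particular zero share nor any length-of-stay assumption. With a common variance, the size of the understatement (factors of 2.8 to 12.5 in three data sets) does depend on the assumed lognormal stays and should be read as illustrative.

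It would be tempting to conclude that the comparison of hospital days between arms is compromised. It is not: the ANOVA and ANCOVA of total days are separate, and monthly severe respiratory illness has its own logistic model. The primary outcomes are descriptive, and the plan expects to be underpowered for efficacy. What is affected is one supplementary longitudinal analysis of one secondary clinical outcome, and any use of it in sizing the next trial.

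**What to change.** Replace the normal mixture and its EM step by a two-part model:

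1. Any respiratory hospital days in the month: a logistic mixed model like the one already in Section 9.4.3, with arm, month and site.
2. Days given admission: a gamma or zero-truncated negative binomial model with arm and site, and month where the data allow. Use standard errors clustered by child, or random effects linked to part 1 if estimable.

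State that part 2 compares arms only among admitted children and is descriptive. State how a stay that crosses a month boundary is counted. Because the schedule in Section 1.3 lists monthly assessments under the intervention arm only, state that admissions are dated from the medical record in both arms.

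The cost is plan wording before the SAP is finalized, with simpler programming. Estimates of days given admission will be imprecise, since only about 30-45 admission-months are expected at one event per year (45 = 540/12 if each admission falls in its own month); the 50% figure would give 59-77 (540 × 0.109 to 540 × 0.143). That limit comes from the sample and applies to any model. The ANOVA of total days needs no change on this account.
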